According to the various interventions stated above, the outcomes of relevance are readmissions (8-12,15,17,22,24-26,28-44), mortality (7,8,10,12,25,27,28,30-32,38-41,44), length of stay (LOS) (12,25,28,29,32,38,41,45), direct discharge from the ED (12,29), time at home (10,25,27,34), duration of readmission (10,25,34) and physical functional status (8,25,27,28,30,31,34,40,43-45). A successful intervention may be reflected in a shorter LOS, lower risk of readmissions, longer time at home, maintained functional status and a shorter duration of readmission. We suggest that a significant and effective intervention under the best circumstances is reflected in these outcomes. Readmissions are usually considered as such, when the admission occurs within 4 hours after and before 30 days after discharge. Among the frail, in-hospital and post-discharge mortality is high, needing frequent assessment. As shown by Pedersen et al. (7), mortality differs with regard to type of dwelling. Former studies have shown a significant and remarkable reduction of LOS (reduction from median 3 days to median 2 days) and an increase from 49 % to 56 % of patients discharged directly from the ED due to the possibility of early follow up by a geriatric team (12). Functional status is of relevance, especially combined with mortality data, since a better survival of the frailest may be combined with a worsened functional status in the total group. Patient Related Outcome Measures (PROMs) will be assessed and added as secondary outcomes during the project. Patient satisfaction and costs are other relevant outcome measures with regards to the triple aim principle, but will not be included in the present Ph.D. project.

Conclusion

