While some previously tested interventions, including CGA and discharge support arrangements, have been futile (25,31,46), we believe that multidisciplinary, tailored interventions used in selected high-risk groups throughout hospitalization and discharge are effective (8,12,29,34,44). Most former studies regarding early follow-up visits and CGA are made in geriatric settings, somewhat distanced to usual care and municipality services. Many previous trials have included patients without looking in particular for frail high-risk patients, thereby probably underestimating the effects of the intervention. It is not known if an early visit by a community nurse would have the same effect as an early geriatric home visit. Selection of elderly patients who will benefit from home visits by a geriatric team after discharge compared with a community nurse visit or usual care may be useful. MPI has been able to predict mortality, LOS (47), and readmissions (48), but has not previously been tested as a selection tool to distinguish between different follow-up methods. It has been suggested that the major effect from early follow-up is more or less independent of the type of follow-up, but is caused by the early visit itself. The type of dwelling may influence the effect of an early visit, since the care setup in some nursing homes may resemble that of a hospital. The level of frailty may influence the effectiveness and efficacy of the different follow-up schemes. Some patients may be chronically frail and their frailty may already have been handled prior to admission, in a way that dilutes the effect of early follow-up visits. The length of stay and other secondary endpoints may rely largely on the planned follow-up approach. The level of frailty predicts the risk of readmission and mortality and can therefore be used as a major indicator when clinicians have to choose between different follow-up approaches.

Objectives

The aim of this study is to investigate the effects of two interventions using CGA and early post-discharge follow-up visits in a population of frail 75+ year-olds compared to usual care. The vision is to find feasible and durable approaches that can improve patient outcome in the transition from hospital to primary health care. We are aiming to identify subjects who will profit the most from each approach.

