As shown in Fig. 2, all intervention group patients are allocated at the time of randomization on the day of admission to receive either early visit from the community nurse (I) or the multidisciplinary geriatric team (II). The randomization is stratified with regard to dwelling (living alone; cohabiting; nursing home) and number of drugs prescribed prior to

admission (0-3, 4-7, 8 or more drugs), and conducted using the randomization function in REDCap (49). Randomization is open throughout the whole admission with the purpose to enable early discharge planning.

Intervention I and II

Both intervention groups are assessed according to CGA, either by the geriatrician and the physiotherapist/geriatric nurse in the ED, or by a multidisciplinary team comprised of geriatricians, specialized nurses, physiotherapists and occupational therapists during hospitalization in the geriatric wards.

- Intervention (I): comprises early follow-up visit from the community nurse within 24 hours after discharge, and the possibility of consulting a nutritionist, thus supplementing usual care services including the possibility of consulting the patients' GP. Responsibility of treatment including implementation of suggested initiatives and any further assessment is handed over to the GP at discharge.
- Intervention (II): CGA is continued during early follow-up by the geriatric team. On weekdays visits are scheduled within 24 hours after discharge. For patients discharged during weekends or holidays, supporting telephone calls are provided by the geriatric team. If needed, the geriatric team nurse visits the patient. The concept of CGA in this stage does not differ from the above-mentioned. There are no standardized demands, but a part of the intervention can be to perform hospital services at home and continued treatment and diagnostics after discharge. The possible services provided by the geriatric team are further described in the geriatric team course description. The responsibility of treatment rests with the geriatric team until dispatch of the discharge summary. Patients then return to usual care. The geriatric team follow-up is planned to last a maximum of 7 days, yet allowing extension for as long as there is a need for services performed exclusively by the geriatric team as described in the geriatric team course description.

Control group

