The patients in the control group are discharged to usual care and do not receive early follow-up visits. Usual care features municipality services and optionally a GP home visit (see Appendix 2). Eligible control patients are consecutively included by a Research Assistant. The estimated level of frailty will be assessed by the PhD-student based on a MPI-screening tool fitted to be performed using only medical record data. This fitted tool will be tested and validated prior to the inclusion of the control group. Clinicians will be blinded to the result of the MPI-screening of the control subjects to ensure that discharge is performed in accordance with usual care.

Outcomes

The primary outcome is readmission within 30 days after discharge. Secondary outcomes are:

- Mortality 30 days after discharge and 90 days after admission
- Length of stay during primary admission and total length of stay including following readmissions
- Direct discharge from the Emergency Department
- Time at home before readmission
- Duration of readmission
- Physical functional status 30 days after discharge (Functional Recovery Score)
- Patient Related Outcome Measures as defined by a focus group of included patients and/or their relatives

Statistical analyses

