Data are registered in REDCap and exported to STATA version 15 for the statistical analyses. Statistical significant results are defined as a p-value of 5% or less. The two intervention groups and the control group will be compared with regard to baseline measures. If needed, statistical corrections for demographical differences and level of frailty will be made. The use of services and other contents of follow-up will be assessed and compared if possible. Baseline data collected for the entire study population before discharge are: age, gender, date of admission, co-habitation status, number of drugs, and level of frailty measured by MPI including functional status by means of Functional Recovery Score (FRS) at discharge. Follow-up data for the control group will be collected on type of planned care after discharge. Follow-up data for the entire study population will be collected on: department of discharge, date of discharge, primary diagnosis at discharge, dwelling after discharge, readmission date, and death date. For the intervention cohort additional data are collected: date of follow-up, provided services after discharge, number and date of visits (team, GP, nurse) after discharge, phone-calls to the geriatric team or GP, nutritionist consultations, FRS after 30 days, date of dispatch of discharge summary. Additional data will be collected by review of the electronic patient records.

Outcomes

A hazard ratio (HR) for readmissions will be calculated using a Cox regression model with death as a 'competing risk' factor. The HRs of readmission with 95% confidence intervals (95% CI) for interventions I and II will be compared individually and to the control group. The interventions will be tested in subgroup analyzes based on: patients discharged directly from the ED, type of dwelling and level of frailty. Median LOS, time at home before readmission and duration of readmission will be calculated and compared using the Wilcoxon rank-sum test. The mortality hazard ratio will be calculated also using the Cox regression model. The change in functional status at discharge and 30 days after discharge will be compared in a linear regression model. Data will be analyzed in accordance with intention-to-treat and per-protocol analysis.

Sample size

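### The 30-day mortality outcome starts at discharge although patients are randomised at admission, so it omits ward deaths and depends on discharge timing

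*Protocol*

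**What the plan says.** The Outcomes section, with the same wording in both documents, lists one mortality line with two clocks: "Mortality 30 days after discharge and 90 days after admission". The Randomization section places allocation at the start of the stay: "all intervention group patients are allocated at the time of randomization on the day of admission". It adds that staff know the allocation from then on: "Randomization is open throughout the whole admission with the purpose to enable early discharge planning".

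Three other statements bear on the point. The Outcome measures section says "Among the frail, in-hospital and post-discharge mortality is high, needing frequent assessment". The background Conclusion says "The length of stay and other secondary endpoints may rely largely on the planned follow-up approach". Length of stay (LOS) and direct discharge from the emergency department are themselves secondary outcomes.

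On analysis, the Statistical analyses section says "The mortality hazard ratio will be calculated also using the Cox regression model" and promises intention-to-treat and per-protocol analyses. It gives no time origin for the mortality model, no denominator for the 30-day rate and no rule for patients who die before discharge.

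**The concern.** An intention-to-treat comparison counts events from randomisation in everyone randomised. Here the 30-day clock starts only when a patient leaves hospital alive, which happens after randomisation and may be influenced by the arm. Two consequences follow.

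- **Omission.** A patient who dies on the ward cannot have the 30-day outcome. No listed outcome shows these deaths separately; they appear only within the 90-day figure.
- **A shifted window.** If one arm discharges earlier, its 30 days cover an earlier stretch of the risk curve. Suppose a patient dies on day 4 after admission. The death counts if discharge was on day 2, and does not count if the patient was still an inpatient.

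At stake is the reading of the only early mortality outcome: whether earlier discharge with team follow-up costs or saves lives in the first weeks. The comparison with the Randers control group has the same weakness if stays differ between hospitals.

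**Working it through.** **1. The plan's own mortality figure.** The Sample size section gives 1,019 per arm for 90-day mortality of 20.6% vs 15.6% (80% power, 5% significance). A two-sided comparison of two proportions with continuity correction gives 970, and 970 × 1.05 = 1,018.5, so the figure reproduces. It rests on the 90-day outcome counted from admission and does not depend on the 30-day clock.

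**2. Inputs.**
- Mean pilot 90-day mortality: (20.6 + 15.6)/2 = 18.1% (Sample size).
- 30-day mortality: 10% (Sample size). It is a planning allowance whose origin is not stated; I take it as counted from admission.
- LOS of 2 vs 3 days: an assumption. The size is borrowed from the earlier study in Outcome measures ("reduction from median 3 days to median 2 days"). The documents give no LOS for intervention I against II.
- Identical death times from admission in both arms, so any difference is artefact.

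**3. Does the death hazard fall?** A constant hazard reaching 18.1% at day 90 would give 1 − 0.819^(1/3) = 6.4% at day 30. The plan's 10% is higher. The implied risk per 30 days between days 30 and 90 is 1 − (0.819/0.900)^(1/2) = 4.6%. These figures suggest a falling hazard.

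**4. Fitted curve.** Weibull: F(t) = 1 − exp(−λt^k).
- k = ln[ln(0.819)/ln(0.900)]/ln 3 = ln(1.895)/ln 3 = 0.582
- λ = −ln(0.819)/90^0.582 = 0.01456
- F(2) = 2.156%, F(3) = 2.721%, F(32) = 10.362%, F(33) = 10.539%

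**5. Apparent 30-day post-discharge mortality.**

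| | Discharge on day 2 | Discharge on day 3 | Difference (points) |
|---|---|---|---|
| In-hospital deaths, F(L) | 2.16% | 2.72% | |
| Of those randomised, F(L+30) − F(L) | 8.21% | 7.82% | 0.39 |
| Of those discharged alive, [F(L+30) − F(L)]/[1 − F(L)] | 8.39% | 8.04% | 0.35 |
| Counted from randomisation, F(30) | 10.0% | 10.0% | 0 |

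With stays spread log-normally around the same medians (log-SD 1.0), in-hospital deaths are 2.5% and 3.2%, and the differences are again 0.39 and 0.35. In an arm of 758, the uncounted deaths in the table are 0.0216 × 758 = 16 and 0.0272 × 758 = 21.

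**6. Dependence on the hazard shape.** Holding F(90) = 18.1% and fixed stays of 2 vs 3 days; a positive value counts against the earlier-discharging arm:

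| Weibull shape | 30-day mortality from admission | Artefact, of those randomised | Artefact, of those discharged alive |
|---|---|---|---|
| 0.4 (falling) | 12.1% | +0.59 | +0.55 |
| 0.7 (falling) | 8.8% | +0.26 | +0.23 |
| 1.0 (constant) | 6.4% | +0.01 | 0 |
| 1.3 (rising) | 4.7% | −0.10 | −0.11 |

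**7. Against sampling error.** At about 8% mortality and 758 per arm, the standard error of the difference is √(2 × 0.08 × 0.92/758) = 1.39 points. A shift of 0.35 to 0.39 is 0.25 to 0.28 standard errors, which raises a two-sided 5% false-positive rate to about 6%.

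**8. Limit of the fit.** If the 10% was counted from discharge after a 3-day stay, none of the Weibull shapes tried (0.05 to 1) with F(90) = 18.1% reproduces it; the closest gives about 8.1%, at shape 0.5. The 10% would still exceed the constant-hazard 6.4%, so the direction stands, but the size in step 5 rests on the admission origin.

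**The case against.** The strongest reply is that the paired outcome already covers the gap. The same line counts 90-day mortality from admission, so every ward death enters there, and the mortality sample size rests on it. That stands, and it confines the problem to one secondary outcome. It does not answer the question about the first weeks.

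Second, the arms' planned care differs mainly after discharge. The primary outcome and functional status also run for 30 days from discharge, and readmission is analysed with death as a competing risk. Post-discharge mortality on that window is a natural companion. This stands too, and it is a reason to keep the outcome as a supporting one rather than reduce it to description.

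Third, a reader might infer that the earlier-discharging arm is bound to look worse. The documents do not support that: the direction needs a death hazard that falls after admission, and the 10% that suggests one has no stated origin.

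Fourth, a reader might carry the cited fall in median LOS over to the randomised arms. That result came from a study of early geriatric visits against GP follow-up about a week after discharge. Here both arms receive the same in-hospital geriatric assessment, both are planned an early visit (within 24 hours; on weekdays for the team arm), and the stated hypothesis is equal LOS. The plan supports only that LOS may depend on the arm.

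Finally, the documents do not call this a safety outcome; it is an early mortality outcome.

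**Conclusion.** The point holds in limited form. The omission of ward deaths and the conditioning on live discharge follow from the wording and the timing of randomisation, whatever the hazard shape. Under the fitted curve and assumed stays of 2 vs 3 days, about 2 to 3% of randomised patients die in hospital uncounted, and identical deaths make the earlier-discharging arm look worse by about 0.3 to 0.4 point (0.2 to 0.6 across the falling-hazard shapes). The artefact is zero among those discharged alive under a constant hazard and reverses under a rising one. These sizes rest on an assumed LOS gap and on a 10% figure of unstated origin. The 90-day outcome and both sample sizes are unaffected. This is a cheap improvement to a secondary outcome, not a threat to the trial's main result.

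**What to change.** In the Outcomes section of both documents, define the between-group early mortality comparison as death within 30 days of randomisation (day of inclusion for the control group), in all included patients. In the Statistical analyses section, start the mortality Cox model at that same origin. Tabulate in-hospital deaths by group. Keep 30-day post-discharge mortality as a supporting outcome on the readmission window, give its denominator, and state that it is conditional on being discharged alive.

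The cost is wording and one more mortality analysis. Admission, discharge and death dates are already collected for the entire study population, and no sample size changes. Comparison with earlier studies that counted from discharge becomes slightly less direct, though the supporting outcome preserves most of it.

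### Covariate adjustment is made only if a baseline comparison seems to call for it, with no criterion, and the randomisation strata are terms in no stated main-effect model

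*Protocol*

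**What the plan says.** In the Protocol, Statistical analyses, the order is a comparison followed by a conditional correction. First, "The two intervention groups and the control group will be compared with regard to baseline measures". Then, "If needed, statistical corrections for demographical differences and level of frailty will be made". The Combined protocol and SAP repeats both sentences, so it does not close the gap. Neither document says what counts as needed, which demographic variables are meant, how frailty would enter, or whether the rule differs between the randomised comparison and the control cohort.

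Under Randomization, both documents state: "The randomization is stratified with regard to dwelling (living alone; cohabiting; nursing home) and number of drugs". The drug bands are 0-3, 4-7 and 8 or more.

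The outcome models name no covariates or strata. For the primary outcome: "A hazard ratio (HR) for readmissions will be calculated using a Cox regression model with death as a 'competing risk' factor". For death: "The mortality hazard ratio will be calculated also using the Cox regression model". Dwelling reappears only as a subgroup factor, and drug count only in the baseline list.

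Most of the data needed are already planned: "Baseline data collected for the entire study population before discharge are: age, gender, date of admission, co-habitation status, number of drugs". The same list includes "functional status by means of Functional Recovery Score (FRS) at discharge". Among the follow-up data are "primary diagnosis at discharge, dwelling after discharge, readmission date, and death date".

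**The concern.** The one rule covers two different comparisons.

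- **I versus II** is randomised and stratified. Omitting the strata does not bias the test, but it gives up a little precision. Letting the baseline table decide on adjustment means that more than one HR could later be presented as primary.
- **Either intervention versus control** is a cohort comparison with patients from another hospital and other municipalities (Design; Study population). A baseline check is a weak safeguard here, because an imbalance too small to trigger it still biases the HR. The Protocol itself says that frailty predicts readmission and mortality (Conclusion of the background). Its second hypothesis is that the three approaches have similar effects, so a bias of a few percent is not irrelevant.

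**Working it through.** **1. The plan's own sample sizes.** Two proportions, two-sided 5%, with continuity correction.
- Readmission, 13.7% vs 8%, 90% power: 624 per arm uncorrected. With the correction, (624/4) × [1 + √(1 + 4/(624 × 0.057))]² ≈ 659, and 659 × 1.15 = 757.9, i.e. 758.
- Mortality, 20.6% vs 15.6%, 80% power: 930 uncorrected, 970 corrected, and 970 × 1.05 = 1,018.5, i.e. 1,019.

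Both stated figures reproduce. They assume an unadjusted comparison, so adjustment does not alter them.

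**2. I versus II.** The documents give no covariate effects, so these are assumed.
- Set-up: 3,000 simulated trials per case, 720 per arm (758 × 0.95), 3 × 3 strata in blocks of 4, readmission 13.7% vs 8.0%, and 10% deaths by 30 days in arm I.
- Assumed shares: dwelling 50/35/15%, drugs 10/35/55%, severe frailty 40%.
- Assumed effects, weak/moderate/strong: frailty HR 1.25/1.75/2.75, with smaller effects for drugs, dwelling, age and gender.
- The full model has strata, MPI level, age and gender.

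| Model | Power unadjusted, % | Power full model, % | Change, points |
|---|---|---|---|
| Cause-specific Cox | 94.3 / 94.2 / 94.4 | 94.2 / 94.3 / 95.7 | -0.1 / +0.1 / +1.3 |
| Subdistribution | 94.2 / 93.4 / 94.5 | 94.2 / 94.1 / 95.7 | 0.0 / +0.7 / +1.2 |

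Type I error was 4.7-5.2% in every case (Monte Carlo SE 0.4 points). A separate simulation used logistic regression as a proxy, with 659 per arm and 5,000 null trials. Each of six plausible fixed models had type I error of 4.6-4.7%; taking the most favourable of the six gave 5.9%.

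**3. Control cohort, one confounder.** The documents give no frailty shares, frailty HR or control group size, and no trigger. Assumed: 40% severe frailty in the intervention group, frailty HR R = 1.5, 2 or 3, 758 per group, trigger p<0.05, no true effect, and frailty measured alike in both groups, so that a flagged imbalance is fully corrected.

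- Chance of a flag for 40% vs 45%: the null SE is √(2 × 0.425 × 0.575/758) = 0.02539 and the SE under the imbalance is √((0.24 + 0.2475)/758) = 0.02536. So z = (0.05 - 1.96 × 0.02539)/0.02536 ≈ 0.01, and the probability is 0.504.
- Null HR if never adjusted: (1 + pI(R-1))/(1 + pC(R-1)). For 40% vs 45% and R = 3, this is 1.8/1.9 = 0.947.
- Average under the triggered rule: that HR raised to the power (1 - chance of a flag). Here 0.947^0.496 = 0.974.

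| Intervention vs control | Chance of a flag | Null HR, never adjusted (R = 1.5 / 2 / 3) | Average null HR, triggered rule |
|---|---|---|---|
| 40% vs 45% | 0.504 | 0.980 / 0.966 / 0.947 | 0.990 / 0.983 / 0.974 |
| 40% vs 35% | 0.520 | 1.021 / 1.037 / 1.059 | 1.010 / 1.018 / 1.028 |
| 40% vs 50% | 0.975 | 0.960 / 0.933 / 0.900 | 0.999 / 0.998 / 0.997 |
| 40% vs 30% | 0.984 | 1.043 / 1.077 / 1.125 | 1.001 / 1.001 / 1.002 |

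For 40% vs 45%, the chance of a flag is 0.625 with 1,516 vs 758 and 0.627 with 1,019 per group. The last column leans high, because samples that escape the trigger tend to show the smaller imbalances.

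**4. Control cohort, four confounders.** 1,500 simulated null comparisons per case, 758 per group, four binary factors each 5 points apart in the same direction.

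| Factor HR | Unadjusted | Adjusted only where p<0.05 | Always adjusted |
|---|---|---|---|
| 1.25 | 0.962 / 1.047 | 0.993 / 1.014 | 1.006 / 1.000 |
| 1.5 | 0.920 / 1.085 | 0.974 / 1.026 | 0.998 / 1.001 |

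Each pair gives controls 5 points higher, then 5 points lower. The trigger leaves about 30% of the bias: ln(0.974/0.998)/ln(0.920/0.998) = 0.024/0.081 ≈ 0.30. False-positive rates were 5.8-9.0% unadjusted, 4.9-6.3% triggered and 4.7-5.9% always adjusted (Monte Carlo SE 0.6 points).

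**The case against.** The plan does intend to correct, and it names demographics and frailty as the things to correct for. Need could be judged by prognostic importance rather than by a p-value. Eligibility restricts both cohorts to MPI 2 or 3, which already limits frailty differences. MPI also contains drug count and social status (Appendix 1A), so a frailty correction would carry part of the strata.

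The effect is also small against sampling error. With about 0.137 × 758 ≈ 104 readmissions per group, the SE of the log HR is about √(2/104) = 0.14. A residual of ln(0.974) = -0.026 is about 0.2 of that. The false-positive rates of the triggered and unconditional rules cannot be told apart.

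These points stand and limit the size of the finding. They do not supply a criterion, and the overlap with MPI helps only if the correction is made.

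Three stronger readings are not supported:
- *The control comparison is biased by 5-10%.* Those values arise only if no adjustment is made. Under the assumed trigger, a 10-point imbalance is caught about 98% of the time.
- *The strata are ignored altogether.* Dwelling is a planned subgroup factor; what is missing is a main-effect term.
- *The records-only frailty tool makes this point larger.* Misclassification in controls is a separate problem that the conditional wording does not cause. The tool is to be validated before controls are included (Control group).

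**Conclusion.** The point holds in a limited form. The missing criterion and the absence of the strata from the stated main-effect models are plain from both documents.

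For I versus II there is no bias. The cost is about 0 to 1.3 points of power under assumed effects, and an open choice of primary HR.

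For the control cohort, a 5-point imbalance in one strong factor would be missed about half the time at 758 per group. The average null HR would be about 0.97-0.99 or 1.01-1.03, and larger imbalances are nearly always caught. This is small beside the cited fall in readmissions from 23% to 12% (a ratio of 0.52), but it bears on a hypothesis of similarity. The direction cannot be inferred, and every control-cohort input, including the p<0.05 trigger, is an assumption. The change is worth making because it costs almost nothing.

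**What to change.** Delete the condition and fix the models before the data are analysed.

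- **I versus II.** Make the primary Cox models for readmission and mortality stratified by, or adjusted for, dwelling and drug count in the bands used for randomisation. Add enrolment MPI level (2 or 3), age and gender as covariates. Report the unadjusted HR as a sensitivity analysis. Do not adjust for Functional Recovery Score at discharge or dwelling after discharge: both are recorded after an allocation that is open during the admission.
- **Control cohort.** Always adjust for age, gender, co-habitation or dwelling, and drug count, whatever the baseline comparison shows, and name this as the primary model. Add frailty level as a pre-stated sensitivity analysis. Control frailty comes from a records-only tool, so adjusting on it may reduce, leave or add bias. State that residual confounding remains, including any frailty difference that the four covariates do not carry.

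**Cost.** This is a change of wording plus the sensitivity analyses. The four control-cohort covariates are already collected for everyone. If all terms are entered as covariates with age linear, the I versus II model uses 2 + 2 + 1 + 1 + 1 = 7 degrees of freedom, against about (0.137 + 0.08) × 659 ≈ 143 expected readmissions. There is some overlap with MPI, which bands drugs differently (0-3, 4-6, 7 or more). The 758 and 1,019 per arm stand.
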